7. DEMOGRAPHICS AND OTHER BASELINE CHARACTERISTICS

Demographic parameters and other baseline characteristics (age at Day 0 vaccination, gender [for infants], ethnicity, race, height [cm], weight [kg]) will be summarized by treatment group and serology cohort (as applicable) for all maternal and infant subjects (separately) in the Safety Population. Descriptive statistics (number of subjects [N], mean, median, minimum and maximum values) will be presented for weight (kg), and height (cm) measurements recorded at Study Day 0. No statistical testing will be performed on these data.

Age (years) at the Day 0 vaccination will be calculated as the closest lower integer result of (date of Study Day 0 vaccination – date of birth) / 365.25, and will be presented as a continuous variable, using descriptive statistics. Age will also be summarized as a categorical variable (e.g., 18 to < 29 years and 29 to \leq 40 years). Gender of infants will be summarized as a categorical variable (e.g., “Male”, “Female”). Ethnicity will be summarized as number and percentage of subjects according to predefined categories (i.e., Hispanic or Latino, not Hispanic or Latino) listed in the eCRF. Race will also be summarized as number and percentage of subjects according to predefined categories (i.e., American Indian or Alaska Native, Asian, Black or African American, Native Hawaiian or Other Pacific Islander, and White).

Continuous variables will be presented by summary statistics (e.g., mean and standard deviation for the non-immunogenicity endpoints, and geometric means and their 95% confidence intervals for the immunogenicity endpoints); APGAR scores and other infant health outcomes at delivery may additionally be summarized as medians and interquartile ranges. Categorical variables will be presented by frequency distributions (frequency percentages for the non-immunogenicity endpoints, and percentages and their 95% confidence intervals for the immunogenicity endpoints).

Medical history and physical examination diagnoses/abnormalities will be coded using MedDRA version 16.1. Baseline medical history and physical examination findings recorded on Day 0 (prior to vaccination) will be summarized separately, by body system, treatment group, and for all maternal subjects in the Safety Population. Within each body system, the number and percentage of subjects with at least one abnormality in that body system will be presented, respectively. Multiple abnormalities within a given body system for a subject will be counted once within that respective body system.

8. EXTENT OF EXPOSURE

8.1. Study Vaccine

Subject vaccination exposure will be summarized as the number and percentage of maternal subjects who received the study vaccine at Day 0. The number of maternal subjects vaccinated at Day 0 will be presented by treatment group and for all subjects. The number of maternal subjects vaccinated by location (right or left deltoid) will be presented in subject data listings.

8.2. Concomitant Medication

The assessment of concomitant medication use by subjects during the study will coincide with the collection period of adverse events for each vaccination; per the protocol, concomitant medication includes prescription and non-prescription drugs or other treatments, and any vaccine other than study vaccines. Concomitant medications recorded on the Concomitant Medications eCRF will be summarized by WHO-DRUG DDE (Enhanced) B2 format September 1, 2013. The number (percentage) of subjects who record one or more concomitant medications will be presented by treatment group for all subjects in the Safety Population. Multiple occurrences of medication usage for a subject will be counted only once within an ATC term and standardized medication name. The presentation of concomitant medications will include all medications recorded on the Concomitant Medications eCRF, including medications with a missing or partial start date or a start date prior to Study Day 0 vaccination. A separate listing of treatment-emergent new concomitant medications will be presented.

9. INTERIM (FUTILITY AND INFORMATIONAL) ANALYSES

An IBG will perform the futility and informational analyses (see Section 14.1 for details on the informational analysis) based on a summary table provided by the DSMB statistician. All futility and informational analyses of efficacy data will include all infant subjects who will be at least 90 days old at the time of the data cutoff date.

10. EFFICACY ANALYSES

A closed sequential testing approach will be adopted for the primary efficacy endpoints to control the Type I error rate for the study. The detailed approach is summarized in Section 16.4 (Multiple Comparisons/Multiplicity).

10.1. Study Definitions of Efficacy Determination

Abbreviation or Term	Definition
RSV LRTI:	Confirmed RSV LRTI will feature detection of RSV in respiratory secretions by RT-PCR and at least one of the following clinical manifestations observed and documented by appropriately-trained study staff: cough, nasal flaring, lower chest wall indrawing, subcostal retractions, abnormal breath sounds (inclusive of stridor, rales, rhonchi, wheezing, and crackles/crepitations); and/or observed apnea.
Medically-significant RSV LRTI:	An RSV LRTI episode with EITHER a resting SpO ₂ < 95% at sea level or < 92% at altitudes > 1800 meters by pulse oximetry on room air OR tachypnea defined as ≥ 70 bpm in an infant 0 to 59 days of age, or ≥ 60 bpm in an infant ≥ 60 days of age.
RSV LRTI with Severe Hypoxemia:	An RSV LRTI episode with a resting SpO ₂ < 92% at sea level or SpO ₂ < 87% at altitudes > 1800 meters by pulse oximetry on room air OR documented use of oxygen by high flow nasal cannula OR a requirement for continuous positive airway pressure (CPAP) OR bilevel positive airway pressure (BiPAP) OR Bubble CPAP OR bag-mask ventilation OR intubation with subsequent mechanical (or manual) ventilation OR extracorporeal membrane oxygenation (ECMO).
RSV Season:	The period spanning the onset/remission of increased confirmed RSV infections in the community based on local surveillance data.
RSV Episode:	The interval between the onset of respiratory symptoms (start date) and the episode stop date with confirmation of RSV infection by RT-PCR of any respiratory secretions collected within this period.
Correlate of Risk:	An immune marker statistically correlated with risk, either absolute or relative to a control population, of meeting an RSV infection clinical endpoint.
Symptomatic RSV infection (maternal subjects)	An acute, clinical study site-observed RSV infection, manifesting as one or more of cough, stuffy nose, runny nose, dyspnea, sore throat, fever, new or increasing wheezing, or new or increasing sputum production; with detection of RSV in respiratory secretions by RT-PCR.

10.2. Clinical Endpoint Adjudication Committee (CEAC)

A clinical endpoint adjudication committee (CEAC) comprising an odd number of three or more clinically-experienced voting pediatricians, a non-voting chair who will oversee meetings of the CEAC, and a non-voting coordinator for administrative support will be empaneled to review all primary, secondary, and exploratory efficacy endpoints relative to infant subjects. The operations of the CEAC will be carried out according to a charter which will be collaboratively drafted by the CEAC and the sponsor, and will be adopted prior to any review CEAC activities. The CEAC will review each potential efficacy endpoint event to determine whether the protocol-specified criteria have been fulfilled in a plausible temporal relationship. All deliberations of the CEAC will be carried out in blinded manner with regard to treatment

assignment and the determination of the CEAC with regard to each endpoint event will be final and binding on the sponsor.

10.3. Analysis of Primary Efficacy Endpoints

The primary efficacy endpoint will be analyzed on the ITT-EFF-I and PP-EFF-I (infant) Populations. Conclusions concerning stopping for futility, the informational analysis, or declaration of attainment of the primary efficacy endpoint at the completion of the study, will only be based on the PP-EFF-I Population. In addition, supportive analyses based on the ITT-EFF-I Population will also be performed.

The Vaccine Efficacy (VE) is defined as $VE (\%) = (1 - RR) \times 100$, where RR = Relative Risk of incidence rates between the two treatment groups (RSV F Vaccine / Placebo). The final analysis will be carried out at one-sided Type I error rate of 0.0124 (i.e., the lower bound of two-sided 97.52% confidence interval). An estimate of vaccine efficacy will be reported using a two-sided 95% confidence interval. This conservative Type I error rate was determined as a part of the original group sequential design (GSD) approach and will be retained to guard against a potential Type I error inflation resulting from the decision to stop the study at ~4,600 maternal subjects given this decision occurred after the informational analysis. Since this change was not part of the original study design at the initiation of the study, the agreement on how to implement the change with respect to Type I error rate was finalized in consultation with the US-FDA.

For the original design using the GSD, a simulation of 5,000 trials was performed under a range of scenarios (including both varying placebo rates of medically-significant RSV LRTI and endpoint event ratios in infants of active vaccinees relative to placebo recipients). A summary of the simulation results is provided in the adaptive design for reference ([APPENDIX 1](#)).

The RR and its CI will be estimated using Poisson regression with Robust error variance [[Zou 2004](#)]. The generalized linear model with unstructured correlation matrix (Robust error variances) will be used. The explanatory variables in the model will include the treatment group. The dependent variable will be the incidence rate of the endpoint of interest. The Robust error variances will be estimated using repeated statement and the subject identifier. Poisson distribution will be used with a link function logarithm.

Hypothesis testing of the primary efficacy endpoint will be carried out sequentially for $H_0: VE \leq 0\%$ and $H_0: VE < 30\%$. Rejection of the first null hypothesis, $H_0: VE \leq 0\%$ demonstrates a statistically significant vaccine effect. Rejection of the second null hypothesis, $H_0: VE < 30\%$ at Type I error rate of 1-sided 0.0124 is required to meet the statistical success criterion pre-specified for the US-FDA. Should success be declared for the primary endpoint through 0 - 90 days of age, the hierarchical sequential analyses of 0 - 120, 0 - 150, and 0 - 180 days of age will be carried out using the Type I error rate of 1-sided 0.025 and the same null hypothesis.

Two types of analyses concerning the primary efficacy endpoint will be performed prior to the final analysis: recurring futility analyses approximately twice per year after the Northern and

Southern hemisphere winter virus season, and an informational analysis with approximately 1/3 of projected subjects enrolled and followed through at least 90 days.

For the futility analyses and the informational analysis, a Bayesian approach will be used and the analyses will be performed by the Independent Biostatistical Group (IBG) as originally designed. An assumption is made that the distribution of the number of events under the vaccine, x_v , and the number of events under placebo, x_p , are binomial:

$$x_v \sim Bin(\pi_v, n_v)$$
$$x_p \sim Bin(\pi_p, n_p)$$

where π_v and n_v , respectively, are the probability of an RSV event and the total number of subjects in the vaccine group and π_p and n_p , respectively, are the probability of an event and the total number of subjects in the placebo group.

Furthermore, we assume prior distributions for π_v and π_p that are flat, non-informative beta distributions:

$$\pi_v \sim Beta(1,1)$$
$$\pi_p \sim Beta(1,1).$$

Futility will be demonstrated under the primary hypothesis based on the posterior probability that the event ratio, $r = \pi_v / \pi_p$, is less than or equal to 0.60.

Given x_v events out of n_v total subjects in the vaccine group and x_p events out of n_p total subjects in the placebo group, the posterior distributions of π_v and π_p are:

$$\pi_v | x_v \sim Beta(1+x_v, 1+(n_v - x_v))$$
$$\pi_p | x_p \sim Beta(1+x_p, 1+(n_p - x_p)).$$

Sampling from the posterior probability distribution for the event ratio is generated by:

1. Sampling 10 million independent values from the posteriors of π_v and π_p
2. Calculating the event ratio, $r = \pi_v / \pi_p$ under each pair-wise sample from the posterior of π_v and π_p .

Futility stopping will be based on the posterior probability of futility that the event ratio is less than or equal to 0.60 is less than or equal to 0.05. Furthermore, an additional constraint governing the ability to stop the trial early for futility requires that a minimum of 10 events be observed in the vaccine arm. All futility analyses will include all infant subjects who are 90 days old at the time of the data cutoff date.

In addition as a sensitivity analysis, time to the first medically-significant RSV LRTI event will be analyzed by treatment group using Kaplan-Meier methods taking potential differences in the length of subject follow-up into account. Sub-analyses will be performed to evaluate vaccine effects on all infections in which RSV is confirmed by RT-PCR, and also infections in which only RSV is found (i.e., no co-infections). The incidence rate of medically-significant RSV LRTI may be generated by age stratum or co-morbidities present, if sufficient event numbers are available.

Sensitivity analyses for the primary efficacy endpoint will be performed to investigate the impact of missing specimens for suspected-RSV illnesses, including RSV-negative specimens collected outside the specified collection window, and clinical assessments, including clinical signs/symptoms, respiratory rates, and pulse oximetry measurements, obtained by non-study healthcare providers (e.g., hospitalization records). Further details are presented in Section 16.8.

10.4. Analysis of Secondary Efficacy Objective

Analysis of secondary efficacy endpoints will be using the frequentist method. The relative risk (RR) and its two-sided 95% CI will be estimated using Poisson regression with robust error variance [Zou 2004]. A generalized linear model with unstructured correlation matrix (robust error variances) will be used. The explanatory variables in the model will include the treatment group. The dependent variable will be the incidence rate. The Robust error variances will be estimated using repeated statement and the subject identifier. Poisson distribution will be used with a link function logarithm. The vaccine efficacy and the corresponding two-sided 95% CI will be calculated.

The null hypothesis, $H_0: VE \leq 0\%$, using the 1-sided Type I error rate (i.e., lower bound of two-sided 95% CI) will be used for analyses of all secondary efficacy endpoints in infants. For each endpoint, in the event that efficacy is shown through the first 90 days of life, a hierarchical sequence of hypothesis tests will be carried out to examine efficacy through 120, 150, and 180 days of life.

Additional efficacy analyses may describe the incidence of symptoms used to define RSV LRTI. Percentages of infant subjects with any RSV-confirmed respiratory illness accompanied with the following events/complaints may be presented by treatment group through six months postpartum: cough, nasal flaring, difficulty breathing, manifesting in any of the following clinical signs or symptoms as lower chest wall indrawing, subcostal retractions, abnormal breath sounds (inclusive of stridor, rales, rhonchi, wheezing, and crackles/crepitations), and/or observed apnea. Time to the first RSV-associated event referenced above will also be analyzed using Kaplan-Meier methods for each event category and by treatment group.

10.5. Exploratory Analyses

Exploratory analysis will be conducted by generating classical two-by-two cross tabulations of all RSV respiratory tract infection endpoints detected by active/passive surveillance in infant and maternal subjects from immunization through six months after delivery and by treatment group. The relative risk (RR) and its two-sided 95% CI will be estimated using Poisson

regression with robust error variance [Zou 2004]. A generalized linear model with unstructured correlation matrix (robust error variances) will be used. The explanatory variables in the model will include the treatment group. The dependent variable will be the incidence rate. The Robust error variances will be estimated using repeated statement and the subject identifier. Poisson distribution will be used with a link function logarithm. The vaccine efficacy, and the corresponding two-sided 95% CI will be calculated. Similar analysis will be conducted to assess the incidence of non-RSV LRTI in infant subjects as detected by active and passive surveillance from vaccination through six months after delivery. Percentages of infants and maternal subjects presenting with respiratory symptoms of non-RSV respiratory viruses detected by RT-PCR will be summarized.

All exploratory efficacy analyses will be conducted against the null hypothesis of $VE \leq 0\%$ (i.e., the $RR \leq 1.00$). For each endpoint, in the event that efficacy is shown through the first 90 days of life, a hierarchical sequence of hypothesis tests will be carried out to examine efficacy through 120, 150, and 180 days of life.

11. IMMUNOGENICITY ANALYSES

Immunogenicity summaries and associated statistical analyses will be based primarily on the PP immunogenicity Populations, i.e., PP-IMM-M for maternal subjects and PP-IMM-I for infant subjects with supportive results derived from the ITT Populations, i.e., ITT-IMM-M for maternal subjects and ITT-IMM-I for infant subjects. No imputation for missing data will be performed. Data will be transformed as appropriate prior to analysis. Please refer to Section 16 for the handling of lower limit of quantitation (LLOQ) for the seroconversion (SCR, definition provided below) analysis.

11.1. Analysis of the Secondary Objectives of Immunogenicity

The principal variables of interest for assessment of immune response to the RSV F vaccine will be anti-F IgG EU and PCA concentrations that will be determined at all prospectively defined time-points as stated below. Additional immunogenicity variables will be RSV/A and B MN titers, which will be measured at the baseline and delivery visits for maternal subjects and at the delivery and D+14, D+35, D+60, D+90, D+120, and D+180 visits for infant subjects. For the analysis of paired immunogenicity measures, geometric mean of fold rise in post-vaccination measures compared to baseline (pre-vaccination) in maternal subjects (GMFR) and geometric mean ratio (GMR) of paired samples over time within a maternal subject, an infant subject, or a maternal and infant subject pair (GMR) will be summarized. GMC, GMEU, GMT, and GMFR/GMR will be calculated as the antilog of the mean and 95% CI of \log_{10} -transformed values. The values reported as below the LLOQ of the assay will be set to half of LLOQ. In addition, seroconversion rates (SCR) based on ≥ 2 - and ≥ 4 -fold rise thresholds and seroresponse rates (SRR) will be calculated as defined below.

The following immunogenicity outcome measures and their 95% CI will be summarized by treatment group.

11.1.1. Anti-F IgG ELISA (EU)

The following parameters will be analyzed for maternal subjects.

- GMEU at baseline (pre-vaccination on Day 0) and post-vaccination on Day 14, at delivery, and postpartum on Days 35 and 180 (as applicable).
- GMFR_{Post/Pre} on post-vaccination Day 14, at delivery, and postpartum on Days 35 and 180 (as applicable).
- GMR_{Cord/MS} on the within-maternal-infant pair for cord blood over maternal serum (MS) at delivery, e.g., GMFR Transplacental Transfer Proportion.
- Seroconversion Rate (SCR) – defined as the proportion of subjects with ≥ 2 -fold and ≥ 4 -fold increases in concentration from baseline, calculated as the proportion (%) of subjects in a particular treatment group with a baseline concentration $<$ LLOQ and a post-vaccination concentration $\geq 2 \times$ LLOQ and $\geq 4 \times$ LLOQ, respectively, or a baseline concentration \geq LLOQ and a ≥ 2 -fold and ≥ 4 -fold, respectively, increase in

post-vaccination concentrations. These response rates will be summarized post-vaccination on Day 14, at delivery, and postpartum on Days 35 and 180 (as applicable).

- Seroresponse rate (SRR) – defined as the proportion (%) of subjects in the RSV F treatment group with an increase in antibody level over a specific time period which is greater than the 95th percentile of antibody response in the absence of active vaccine based on the behavior of placebo recipients' sera over the same period. SRR will be analyzed by computing the ratio (post-vaccination/pre-vaccination [Day 0]) at each post-vaccination time-point on Day 14, at delivery, and postpartum on Days 35 and 180 (as applicable). At a given time-point, the 95th percentile of the ratios in the placebo group will be estimated. A subject in any treatment group will be identified as a responder if its ratio is greater than the estimated threshold in the placebo group at the given time-point.

The following parameters will be analyzed for infant subjects:

- GMEU of anti-F IgG in cord blood and on D+14, D+35, D+60, D+90, D+112, and D+180.
- GMR_{AD/Cord} of anti-F IgG EU within-subject ratios after delivery (AD) on D+14, D+35, D+60, D+90, D+120, and D+180 over cord blood value at delivery.
- SRR for infant subjects will be analyzed at a given time-point by estimating the 95th percentile of the EU levels in the placebo group. An infant subject in any treatment group will be identified as a responder if its EU level is greater than the estimated threshold in the placebo group at the given time-point.

11.1.2. Palivizumab-competitive Antibody (PCA) ELISA (µg/mL)

For maternal subjects:

- The same parameters described in Section 11.1.1 will be analyzed. The GMEU for the anti-F IgG will be replaced by geometric mean concentration (GMC) in µg/mL for the PCA ELISA.

For infant subjects:

- The same parameters analyzed described in Section 11.1.1 will be analyzed. The GMEU for the anti-F IgG will be replaced by geometric mean concentration (GMC) in µg/mL for the PCA ELISA.

11.1.3. RSV/A and RSV/B Microneutralization (MN) Titers

For maternal and infant subjects: GMT, GMFR/GMR, and SRR, as described above and for the same time-points referenced above for the anti-F IgG ELISA. For maternal subjects only, SCR will be calculated as defined as the proportion of subjects with ≥ 2 -fold and ≥ 4 -fold increases in titers from baseline to post-vaccination using the same approach as anti-F IgG ELISA.

11.1.4. Infants Antibody Decay Modeling

To estimate the decay of antibody levels in per protocol infants (PP-IMM-I) that result from RSV F protein vaccine immunization in pregnant women, the log10 transformed antibody

levels will be used as the independent variable and the actual age of infant subjects in days at the time of sample collection as the exploratory variable in the regression analysis. The estimated slope will be used to estimate the half-life as $\log_{10}(2)/\text{slope}$ with the corresponding 2-sided 95% confidence interval. All observed values, except for the measures reported as < LLOQ, for each time-point and infant cohort (Phlebotomy Cohort 1, Cohort 2, and Cohort 3) will be pooled to assess the persistence of anti-F IgG antibody, PCA, and/or MN levels over time. Since values reported as < LLOQ do not provide the exact time when the values crossed the LLOQ, they will be excluded from the half-life estimation. All measurements from subjects with at least two \geq LLOQ measures will be included in the analysis. A conventional first order antibody decay model will be used for analysis. A second order or other, more complex, antibody decay model may be further developed to explain the rate of decay of antibody levels in the infants in the study, albeit the dataset may not be sufficiently rich to support more complex models.

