10.5 Immunogenicity Analyses

Immunologic analyses will be conducted using the ITT and PP Populations, with primary conclusions drawn from the PP Population. The primary variable of interest for assessment of immune response to the RSV F vaccine will be anti-F IgG EU and PCA concentration, and testing by these methodologies will have the highest priority. The secondary variables will be RSV/A and B MN titers, which will be determined on all blood samples, but with priority testing assigned to samples collected at the following time-points: at delivery for the maternal subject, and at delivery, D+14, D+35, D+60, D+90, D+120, and D+180 for the infant subject.

The following immunogenicity outcome measures and their 95% CI will be summarized by treatment group. Immunogenicity analyses will be descriptive and include tabulations by treatment group.

Maternal Subjects:

- 1) GMEU or GMC, GMFR, proportion of subjects with ≥ 2 -fold and ≥ 4 -fold increases in EU/concentration from baseline (2- and 4-fold seroconversion rates [SCR]); and SRR of anti-RSV F IgG and PCA at baseline, post-immunization on Day 14, at delivery, and postpartum on Days 35 and 180.

- 2) GMT, GMFR, proportion of subjects with \geq 2-fold and \geq 4-fold increases in titer from baseline (2- and 4-fold seroconversion rates {SCR}); and SRR of RSV/A and B MN titers at baseline and delivery.
- 3) GMFR Transplacental Transfer Proportion, the anti-RSV F IgG GMEU, PCA GMC, and RSV/A and B MN GMT of the within-maternal-infant pair ratios for cord blood over maternal serum (MS) at delivery (GMFR_{Cord/MS}).

Infant Subjects:

- 1) GMEU, GMC, or GMT; and SRR of anti-RSV F IgG, PCA, and RSV/A and B MN antibodies in cord blood and on D+14, D+35, D+60, D+90, D+120, and D+180.
- 2) GMFR of anti-RSV F IgG GMEU, PCA GMC, and RSV/A and B MN GMT within-subject ratios after delivery (D) on D+14, D+35, D+60, D+90, D+120, and D+180 over cord blood value at delivery (GMFR_{AD/Cord}).
- 3) Exploratory modeling of anti-RSV F antibody decay in infants using first order models and infant data.

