4.1.2. Secondary Objectives

The secondary objectives of this study are:

- To determine the efficacy of maternal immunization with the RSV F vaccine in reducing the incidence in infants of:
 - RSV LRTI with EITHER severe hypoxemia (SpO_2 < 92% at sea level or < 87% at altitudes > 1800 meters) or the documented use of oxygen by high flow nasal cannula OR a requirement for continuous positive airway pressure (CPAP) or bilevel positive airway pressure (BiPAP) OR Bubble CPAP OR bag-mask ventilation OR intubation with subsequent mechanical (or manual) ventilation OR extracorporeal membrane oxygenation (ECMO), through the first 90 days of life in infants of maternal RSV F vaccinees as compared to placebo recipients. In the event that efficacy is shown through the first 90 days of life, a hierarchical sequence of hypothesis tests will be carried out to examine efficacy at 120, 150, and 180 days of life.
 - RSV LRTI leading to hospitalization through the first 90 days of life in infants of maternal RSV F vaccinees as compared to placebo recipients. In the event that efficacy is shown through the first 90 days of life, a hierarchical sequence of hypothesis tests will be carried out to examine efficacy through 120, 150, and 180 days of life.

The two secondary efficacy objectives will be evaluated in term infants (≥ 37 weeks gestational age at delivery) born to maternal subjects who received a study injection ≥ 2 weeks (14 days) prior to delivery. Infants with multiple RSV episodes meeting a given criterion will be counted

only once, using data from the first episode. Success under the secondary efficacy hypotheses will be achieved by demonstration of a lower bound of a two-sided 95% confidence interval for the estimate of vaccine efficacy which exceeds 0%.

- To describe the immunologic responses to the RSV F vaccine in healthy maternal subjects, in the third trimester of pregnancies deemed to be at low risk of obstetrical complications, through delivery and six months thereafter.
- To describe the transplacental transfer of maternal antibodies specific for RSV and its F protein based on the ratio of levels in maternal and cord blood at delivery.
- To estimate the rate of decay of RSV and F protein-specific antibodies in infants through the first six months of life.
- To develop an immune correlate of risk of the RSV LRTI syndromes in infants based on anti-F protein antibody and/or palivizumab-competitive antibody levels measured in the infant and/or cord blood.

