18.2. List of Changes from Version 5.0 to Version 6.0

The following changes were made the SAP; no corresponding updates to Version 10 of Protocol RSV-M-301 were required based on these changes.

- Minor wording changes to the Introduction, Study Design, and Major Protocol Deviations Assessment sections to be consistent with the protocol. (Section 1, 2, and 5.3.3.1)
- Wording changes were made to the ITT analysis population definitions to clarify that the mother does not have to have data for the infant, and vice versa. (Section 5.2)
- Updated to clarify the delivery serology sample window for the PP-IMM-M population (Section 5.3.2)
- Category of major protocol deviation involving receipt of any non-protocol vaccine was updated to reflect the current protocol (Section 5.3.3.1)
- Clarified that the protocol deviation listing does not have to be for maternal/infant pairs, but rather for all subjects. (Section 6)

- Added that APGAR scores will additionally be summarized as medians and interquartile ranges. (Section 7)
- Dictionary used to code medical history and unsolicited AEs has been updated (Section 7, 12.1, and 16)
- Dictionary used to code the concomitant medication has been updated (Section 8.2)
- Updated the analysis approach for the infant antibody decay modeling. Instead of using the target visit day for all samples, the actual age of infant subjects in days at the time of sample collection will be used as the exploratory variable in the regression analysis. Also since values reported as < LLOQ do not provide the exact time when the values crossed the LLOQ, they will be excluded from the half-life estimation. (Section 11.1.4)
- Updated how the seroconversion rates are determined (Section 11.1.3) and titers below the LLOQs are handled for the Microneutralization assays that are to be reported in International Units (Section 16)

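### SAP 11.1.4 labels antibody level as the independent variable and omits the minus sign from the half-life formula, so the printed rule gives either a quantity that is not a time or a negative half-life

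*SAP*

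**What the plan says.** SAP 4.1.2 lists among the secondary objectives: "To estimate the rate of decay of RSV and F protein-specific antibodies in infants through the first six months of life". Protocol 2.2 carries the same objective.

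The method is in SAP 11.1.4. Of the log10-transformed antibody data it says "levels will be used as the independent variable and the actual age of infant subjects in days at the time of sample collection", and the sentence continues "as the exploratory variable in the regression analysis". No dependent variable is named. The section goes on: "The estimated slope will be used to estimate the half-life as" log10(2)/slope, with a two-sided 95% confidence interval. The formula has no minus sign and no absolute value. The section also states: "A conventional first order antibody decay model will be used for analysis". The rule covers anti-F IgG, palivizumab-competitive antibody and/or microneutralization results in the per-protocol immunogenicity infants.

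Protocol 10.5 describes the analysis only as "Exploratory modeling of anti-RSV F antibody decay in infants using first order models and infant data". It gives no formula, axis or sign. The Protocol synopsis likewise mentions first-order modelling for half-life estimation and no more. SAP 11.1.4 therefore holds the only half-life formula in either document.

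**The concern.** A half-life comes from the slope of log antibody against time, and that slope is negative when antibody declines. SAP 11.1.4 departs from this in two ways. It calls antibody level the independent variable, which reverses the axes if taken at its word. It also divides log10(2) by the slope without changing the sign. A programmer who follows the section exactly cannot produce a half-life, and one who corrects only the axes produces a negative one. The confidence interval has no separate rule, so it inherits the same fault.

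What is at stake is the stated method for a secondary immunogenicity result. As it stands, whoever programs the analysis has to depart from the approved text without saying so in order to report a sensible number.

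**Working it through.** Neither document states a half-life, a slope or a precision for this analysis, so there is no planned figure to reproduce. The check is algebra, illustrated with assumed half-lives.

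**Inputs.** From SAP 11.1.4: log10 level labelled independent, age in days as the other variable, a first-order model, half-life = log10(2)/slope. Assumed, and not in the documents: true half-lives of 20, 30, 40 and 60 days.

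**Correct formula.** First-order decay is log10(level) = a + b × age, with b < 0. Over one half-life T the level halves, so b × T = -log10(2) and T = -log10(2)/b.

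**Reading 1, literal axes (age regressed on log10 level).** Without noise the slope is 1/b, in days per log10 unit. The printed formula gives log10(2)/(1/b) = log10(2) × b. With log10(2) as a pure number, this is in log10 units per day. It is a multiple of the decay rate and not a time.

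**Reading 2, first-order axes (log10 level regressed on age).** The slope is b. The printed formula gives log10(2)/b = -T.

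**Reading 3, first-order axes with the sign corrected.** -log10(2)/b = T.

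**Worked example, T = 40 days.** log10(2) = 0.30103, so b = -0.30103/40 = -0.00753 log10 units per day, and 1/b = -132.88 days per log10 unit.

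- Reading 1: 0.30103/(-132.88) = -0.00227.
- Reading 2: 0.30103/(-0.00753) = -40.0 days.
- Reading 3: +40.0 days.

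The same calculation over the assumed range, without noise:

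| Assumed half-life (days) | Slope b, level on age | Slope, age on level | Reading 1 | Reading 2 (days) | Reading 3 (days) |
|---|---|---|---|---|---|
| 20 | -0.01505 | -66.44 | -0.00453 | -20 | 20 |
| 30 | -0.01003 | -99.66 | -0.00302 | -30 | 30 |
| 40 | -0.00753 | -132.88 | -0.00227 | -40 | 40 |
| 60 | -0.00502 | -199.32 | -0.00151 | -60 | 60 |

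**Confidence limits.** Let the slope limits be L < U < 0. The printed formula gives log10(2)/L and log10(2)/U. Both are negative, and the limit from L is the larger, so the order is reversed. Applying -log10(2)/x gives two positive limits in the right order.

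One simulated example used 900 infants with cord blood taken as day 0, plus the cohort sampling days in Protocol 7.2 (14/90, 35/120, 60/180). The assumed half-life was 40 days, with log10 SD 0.2 between infants and 0.1 residual. Fitting log10 level on age by ordinary least squares, with within-infant correlation ignored, the corrected formula gave 40.2 days (39.4 to 41.0). The printed formula on the same fit gives -40.2 days, with limits -39.4 and -41.0.

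**The case against.** The strongest reply is that nobody would be misled. The same sentence that calls antibody level independent gives age the role of the exploratory variable, evidently a slip for explanatory, so age is the regressor. The section names a conventional first-order model, which means log level on time. The change list in SAP 18.2, cited here only as context, also treats age this way: "the actual age of infant subjects in days at the time of sample collection will be used as the exploratory variable". On this view *independent* is a slip for *dependent*, a competent programmer would see it, and a negative half-life would be noticed on sight. Decay is also tabulated without this formula, through the within-infant ratios to cord blood in SAP 11.1.1. Protocol 10.5 calls the modelling exploratory and the immunogenicity analyses descriptive.

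Most of this stands. The intended axes are recoverable, and with those axes only the sign is wrong. That age becomes the response is itself an inference, since no dependent variable is named. What does not stand is that the text can be left alone: the missing minus sign is wrong on the intended axes too, and no other passage supplies it.

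A reader might go further and infer that the plan would make maternal antibody appear to wane faster than it does. That would require keeping the reversed axes and multiplying log10(2) by the absolute slope. No such formula appears in the SAP, it conflicts with the first-order model the section names, and the size of any shortfall would rest wholly on assumed variances. The documents do not support that claim.

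**Conclusion.** The point holds as a minor drafting error in an operative rule. Taken literally, SAP 11.1.4 yields a quantity in log10 units per day. On the evidently intended first-order axes it yields a half-life of the right magnitude with a negative sign, and confidence limits that are negative and in reverse order. This conclusion needs only that antibody declines with age; the half-lives and SDs used above are illustrations.

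The consequence is limited to a descriptive analysis serving a secondary objective. No efficacy test, Type I error allocation, success criterion or sample size depends on it, and nothing here suggests that the efficacy conclusions or the reported direction of waning would be affected.

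**What to change.** In SAP 11.1.4, state that log10 antibody level is the dependent variable and actual age in days the explanatory variable. State that half-life = -log10(2)/slope, with the 95% confidence limits obtained by applying -log10(2)/x to the confidence limits of the slope. This transformation of the limits presumes that both slope limits are below zero.

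The change is two phrases of SAP wording. It needs no new data and no additional analysis.
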